6.7. Statistical software

Except for the predictive and PC analyses, statistical analyses will be performed using SPSS version 23 (IBM Corp. Released 2015. IBM SPSS Statistics for Windows, Version 23.0. Armonk, New York: IBM Corp) and Stata version 15.1 (StataCorp. 2017. College Station, Texas: StataCorp LLC).

All predictive and PC analyses were performed using R versions 3.3.3 and 3.5.0 Pre-Release (The R Foundation for Statistical Computing; Vienna, Austria).

7. Discussion

The overall aims of the SICS-I study are to address the diagnostic and prognostic value of clinical examination findings, haemodynamic variables, and biochemical values. This broad aim resulted in multiple research questions and hypotheses, which results in many variables to be tested repetitively. We drafted this SAP to avoid outcome reporting bias and data-driven results. This plan only addresses the hypotheses of the basic study which is, according to our sample size calculations, able to detect a 5% difference for the primary outcomes. Results of the sub-studies will be published as separate manuscripts and SAPs will be written before analysing their hypotheses.

We strive to eliminate inflated type I error rates by adjusting our primary outcomes for different confounders. We also strive to reduce the chance of a type I error due to multiplicity by pragmatically adjusting the P-value as proposed by Jakobsen et al. (12). This adjustment for multiplicity is based on the number of different primary outcomes of the basic study and sub-studies. In each manuscript, we will identify and discuss dubious significant findings. Although we will adjust for multiple testing, we will emphasise the hypothesis-generating aspect of results.

Our diagnostic hypotheses will be tested in two steps: first, we will investigate the association of cardiac index with clinical examination variables and second, we will investigate at which cardiac index the clinical examination findings of hypoperfusion become apparent. We aim to present a cut-off for low cardiac index relevant to critically ill patients in our secondary outcome, as current cut-offs for low cardiac index are based on patients with acute lung injury, heart failure or after cardiac surgery (16-20). Diagnostic test accuracies will be described for each finding or combinations of findings for our proposed cut-off of cardiac index. This secondary analysis, as well as the predefined subgroup analyses, will be considered exploratory and we will emphasise the need for validation in an independent cohort.

8. Conclusion

This SAP presents the principles of analysis of the SICS-I cohort and discusses its major methodologic and statistical concerns. We hope that the results of the SICS-I will be as transparent and robust as possible, so that we minimised the risk of outcome reporting bias and data-driven results.

9. Tables and figures

Figure 1. Flow diagram (example)

[figure not shown]
[figure not shown]
[figure not shown]

Figure 2. Representation of a linear and a radial hyperplane in a Support Vector Machine classifier.

Class 1: squares, class 2: circles, and in blue the boundary cases.

Figure 3. Representation of a Random Forest classifier, with n trees

The circles represent the nodes, with the red and green circles signalling the terminal nodes, and the arrows show the “optimal split” computed for each node of each tree. The aggregated vote of all (n) trees is then combined and expressed as a final classification, for example, “alive”.

Table 1. Specific research questions with add-on measurements

Short title	Research questions	Primary outcome
Basic study	Which combination of clinical variables obtainable through physical examination is associated with cardiac output measured by critical care ultrasonography (CCUS)? Which combination of clinical and haemodynamic variables is associated with 7-day, 30-day and 90-day mortality?	Cardiac output Mortality
1. NIRS	Which clinical examination, biochemical, and haemodynamic variables are associated with tissue (muscle) oxygen saturation (StO ₂) measured by near-infrared spectroscopy (NIRS)? Does the NIRS measurement at the knee have a better association with the clinical and haemodynamic variables compared to the NIRS measurement at the thenar muscle? Is StO ₂ measured by NIRS associated with 90-day mortality?	StO ₂
2. Pulmonary ultrasound	What is the diagnostic accuracy of pulmonary oedema measured with pulmonary ultrasonography and auscultation for pulmonary crackles compared to pulmonary oedema diagnosed on a chest radiograph? Is there a statistically and clinically significant difference in cardiac output between patients with and without a B-profile?	Pulmonary edema
3. PEEP-challenge	Is an increase in positive end-expiratory pressure (PEEP) associated with a decrease in cardiac output?	Cardiac output
4. RV-function & mortality	Is right ventricular (RV)-function measured by the tricuspid annular plane systolic excursion (TAPSE) and peak tissue Doppler systolic velocity in the tricuspid annulus (RV s') associated with 90-day mortality? Is RV-function measured by TAPSE or RV s' associated with clinical examination and cardiac output?	Mortality
5. Abdominal flow	Is peripheral blood flow measured with CCUS associated with cardiac output? Is a proxy for abdominal organ blood flow associated with acute kidney injury (AKI) or 90-day mortality?	Cardiac output
6. FloTrac**	What is the level of agreement between cardiac output measured by the FloTrac compared to cardiac output measured with CCUS? Do the levels of agreement change when factors that might influence FloTrac measurements are present?	Cardiac output
7. Repeated measurements	Are changes in clinical examination findings over 24 hours associated with changes in cardiac output? Are changes in clinical examination, haemodynamic and biochemical variables over 24 hours associated with 90-day mortality?	Cardiac output

8. RV-function & AKI	
Is RV-volume overload measured by tricuspid insufficiency and RV-diameters associated with acute kidney injury?
 
Are clinical examination, biochemical, and haemodynamic variables associated with the development of AKI in patients without known pre-existent chronic kidney disease?
	Acute kidney injury
9. Fluid responsiveness	
What is the diagnostic accuracy of fluid responsiveness assessed by changes in end-tidal carbon dioxide (EtCO₂), heart rate and blood pressure compared to fluid responsiveness assessed by the passive leg raising (PLR) test?
 
What is the diagnostic accuracy of fluid responsiveness assessed by a PLR test without lowering the head of the bed compared to fluid responsiveness assessed by the standard PLR test?
	Cardiac output
10. ARDS	
What is the diagnostic accuracy of a B-profile measured with pulmonary ultrasonography compared to bilateral consolidations assessed on chest radiography for the diagnosis of acute respiratory distress syndrome (ARDS)?
 
Are B-lines measured with pulmonary ultrasonography associated with clinical examination, biochemical, and haemodynamic variables?
	ARDS
11. Myocardial strain	
Is left ventricular (LV) and RV-myocardial strain measured with tissue Doppler imaging associated with 90-day mortality?
 
Is left ventricular (LV) and RV-myocardial strain associated with and conventional CCUS measurements?
 
What is the level of agreement between myocardial strain measured with tissue Doppler imaging and myocardial strain rate measured with speckle tracking?
	Mortality

* B-profile: A B-profile is a strong indicator of pulmonary oedema and is present when three or more B lines are seen in at least three of the six BLUE points, or in two of the four lower BLUE points.

** FloTrac: the FloTrac (Edwards Lifesciences, Irvine, California, USA) is a pulse contour technique which analyses the arterial pressure waveform to compute stroke volume and cardiac output. The technique consists a dedicated pressure sensor (FloTrac) and a monitor to compute stroke volume and cardiac output (Vigileo).

Table 2. Overview of all variables measured in the basic study and the sub-studies.

Variable	Basic study or substudy #	Baseline	After 24 hours	After 3 days	At 90 days	Retrospective
Clinical examination						
Examination date	B	X	X			
Examination time	B	X	X			
Gender	B	X				
Age	B	X				
Height	B	X				
Weight	B	X				
Respiratory rate	B, 7	X	X			
Heart rate and rhythm	B, 3, 6, 7, 9	X	X			
Intra-arterial blood pressures	B, 3, 6, 7, 9	X	X			
Non-invasive blood pressures	B	X				
Central venous pressure	B, 3, 6, 7, 9	X	X			
Urine output in 1 and 6 hours	B, 7	X	X			
Inotropic type, dose, speed	B, 6, 7	X	X			
Mechanical ventilation, ventilator settings	B, 3, 7, 9, 10	X	X			
AVPU score	B	X	X			
Sedative type, dose, speed	B	X	X			
Auscultation: souffles	B, 2, 7, 10	X	X			
Auscultation: crepitations	B, 2, 7, 10	X	X			
Auscultation: rhonchi	B, 2, 10	X	X			
Capillary refill: sternum	B, 7	X	X			
Capillary refill: index finger	B, 7	X	X			
Capillary refill: knee	B, 1, 7	X	X			
Temperature: subjective	B, 7	X	X			
Temperature: central	B, 7	X	X			

Temperature: peripheral at big toe and dorsum of foot	B, 7	X	X			
ΔTemp: central-to-peripheral	B, 7	X	X			
Mottling score at the knee	B, 1, 6, 7	X	X			
Peripheral circulation estimation	B, 7	X	X			
Pump function estimation	B, 7	X	X			
Degree of training	B, 7	X	X			
Haemodynamic variables measured with CCUS						
LVOT diameter	B, 6	X				X (validation in Corelab)
Peak flow velocity	B, 6, 7	X	X			X (validation in Corelab)
Velocity time integral	B, 6, 7	X	X			X (validation in Corelab)
Heart rate (echo)	B, 6, 7	X	X			X (validation in Corelab)
Cardiac output	B, 2, 3, 6, 7, 9, 10	X	X			X (validation in Corelab)
Cardiac output, every hour	6	X (during 6 hours)				
B-lines on 6 locations	2, 4, 7, 10	X	X			
TAPSE	2, 7, 8	X	X			
RV S'	2, 7, 8	X	X			
Common carotid artery diameter, flow	5	X				
Subclavian artery diameter, flow	5	X				
Common femoral artery, diameter, flow	5	X				
Abdominal flow	5	X				
RV basal diameter	8	X				
RV mid cavity diameter	8	X				
RV longitudinal diameter	8	X				
Tricuspid regurgitation peak velocity	8	X				
Left myocardial strain (rate)	11	X				

Septal myocardial strain (rate)	11	X				
Right myocardial strain (rate)	11	X				
Other haemodynamic measurement devices						
NIRS: StO ₂ thenar & knee	1	X				
FloTrac: inclusion date and time	6, 7	X (during 6 hours)	X			
FloTrac: cardiac output every hour	6, 7	X (during 6 hours)	X (once)			
FloTrac: noradrenaline dose	6, 7	X (during 6 hours)	X (once)			
FloTrac: inotropic type, dose, and speed	6, 7	X (during 6 hours)	X (once)			
FloTrac: mottling score	6, 7	X (during 6 hours)	X (once)			
Additional clinical variables						
ICU admission date	B			X		
ICU admission time	B			X		
EMV score	B			X		
Admission reason	B			X		
Patient admission specifics	B			X		
Shock type	B			X		
Final diagnosis	B			X		
X-Ray measurements	B			X		X
ECG measurements	B			X		X
Respiratory distress	10			X		
Direct ARDS risk factors	10			X		
Indirect ARDS risk factors	10			X		
SOFA score						X
SAPS II score						X
APACHE II score						X

APACHE IV score						X
Total ICU stay						X
Medical history						X
Biochemical variables						
Arterial blood gas variables	B			X		
Serum leucocytes	B			X		
Serum hematocrit	B			X		
Serum thrombocytes	B			X		
Serum NT-proBNP	B			X		
Serum hs-troponin T	B			X		
Serum ASAT, ALAT	B			X		
Serum total and direct bilirubin	B			X		
Serum and urine creatinine	B, 8			X		
Serum and urine urea	B			X		
Serum and urine albumin	B			X		
Urine total volume and hours of collection	B, 8			X		
Follow-up						
Mortality in-ICU	All				X	
Mortality reason	All				X	
Mortality 7 day	All				X	
Mortality 30 day	All				X	
Mortality 90 day	All				X	

Table 3. Summary of the hyper-parameters of the three algorithms used for predictive modeling

Algorithm	Parameters	Definition
Gradient Boosted Machine	n.trees	Determines the number of trees (iterations) generated by the algorithm.
	n.minobsnode	Defines the minimum number of observations in the terminal nodes of a tree.
	interaction depth	Defines the number of terminal nodes or leaves of a tree.
	shrinkage	Controls the learning rate of the algorithm.
Random Forest	ntree	Defines the number of trees built by the algorithm.
	mtry	Defines the number of candidate variables randomly selected and tried at each split of a tree.
Support Vector Machine	cost (C)	Controls the misclassification tolerance.
	sigma (σ)	Defines how much a single training example influences the model (a higher sigma constrains the model towards linear).

10. References

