3.2.1. Diagnostic study

We are planning our main analysis with 1075 patients in which we will regress their values of cardiac index against clinical examination findings. For this power calculation, we used the clinical examination variables urine output and capillary refill time as an example (7). In our design paper, the SD of cardiac index was 0.99 and the SD of urine output was 0.98, with a slope estimate of 0.040 obtained when cardiac index was regressed against urine output. The SD of capillary refill time was 2.4, with a slope estimate of -0.045 obtained when cardiac index was regressed against capillary refill time. If the true slope of the line obtained by regressing cardiac index against urine output or capillary refill time is 0.10, we will be able to reject the null hypothesis that this slope equals zero with probability (power) 0.81 for urine output, and 1.00 for capillary refill time. The type I error probability associated with this test of this null hypothesis is 0.015 (see paragraph 6.6 below).

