3.2.2. Prognostic study

We are planning our main analysis with 1075 patients and take skin mottling as an example for our power calculation: in our design paper, 46% of the patients has skin mottling. If we assume a similar proportion in our total cohort, we have 495 patients with skin mottling and 580 without. Pilot data from our design paper indicate that the 30-day mortality proportion among controls is 0.18 (7). If the true mortality proportion for patients with skin mottling is 0.27, we will be able to reject the null

hypothesis that the mortality proportion for patients with skin mottling and control patients are equal with probability (power) 0.84. The type I error probability associated with this test of this null hypothesis is 0.015. We will use an uncorrected chi-squared statistic to evaluate this null hypothesis.

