6.1. Outcome definitions

6.1.1. Primary and secondary outcomes

The research questions and the design of the study have been published (7). We elaborate on the outcomes of the basic study below and described the primary outcomes of each sub-study in appendix 1.

The outcomes of research question 1, i.e. the diagnostic study, are:

- Primary: the association of a single or combination of clinical examination findings with cardiac index measured by CCUS
- Secondary: the diagnostic test accuracy of a single or a combination of clinical examination findings to diagnose a low, normal and high cardiac index
- Secondary: the association and diagnostic test accuracy of a single or combination of clinical examination findings with cardiac index in clinically different patient subgroups

The outcomes of research question 2, i.e. the prognostic study, are:

- Primary: the association of all measured clinical examination, biochemical and haemodynamic variables with 90-day mortality
- Secondary: the association of clinical examination, biochemical and haemodynamic variables with 7-day and 30-day mortality
- Secondary: the association of clinical examination, biochemical and haemodynamic variables that are not visible to caregivers with 90-day mortality
- Secondary: the association of clinical examination, biochemical and haemodynamic variables with 90-day mortality in clinically different patient subgroups

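### Section 7 claims the basic study can detect a 5% difference, but Section 3.2 contains no such calculation and power for a 5-point rise in mortality is only about 0.26 to 0.34

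*SAP*

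**What the plan says.** Section 7 (Discussion) sums up the basic study as "according to our sample size calculations, able to detect a 5% difference for the primary outcomes". It does not say whether 5% is absolute or relative, or what it would mean for cardiac index.

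The calculations it points to are in Section 3.2:

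- **Diagnostic study (3.2.1).** The effect is a regression slope: "If the true slope of the line obtained by regressing cardiac index against urine output or capillary refill time is 0.10". Stated power is 0.81 for urine output and 1.00 for capillary refill time, with 1075 patients and a type I error of 0.015.
- **Prognostic study (3.2.2).** Skin mottling is the example: "we have 495 patients with skin mottling and 580 without". The control rate is a 30-day figure: "Pilot data from our design paper indicate that the 30-day mortality proportion among controls is 0.18". The alternative is "If the true mortality proportion for patients with skin mottling is 0.27". Stated power is 0.84 at 0.015 with an uncorrected chi-squared test.

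Section 6.1.1 defines the prognostic outcomes as "Primary: the association of all measured clinical examination, biochemical and haemodynamic variables with 90-day mortality" and "Secondary: the association of clinical examination, biochemical and haemodynamic variables with 7-day and 30-day mortality".

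**The concern.** Section 7 attributes a result to calculations that do not contain it. The mortality example concerns 9 points, not 5, and a regression slope is not a percentage difference. The only mortality calculation also uses 30 days, a secondary time point, so the primary prognostic outcome has no power figure.

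The cohort size is fixed, so the sentence cannot lead to a wrong sample size. What it affects is interpretation. A reader who trusts it could take a non-significant finding as evidence against a 5-point mortality difference, when the study would more often than not miss one.

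**Working it through.** **Inputs.** From 3.2.2: n = 580 without and 495 with mottling; 30-day control mortality 0.18; alternative 0.27; alpha 0.015; uncorrected chi-squared test. Sidedness is not stated; two-sided is assumed, so z = 2.432. From 3.2.1: n = 1075; SD of cardiac index 0.99; SD of urine output 0.98; SD of capillary refill time 2.4; slope 0.10. From Appendix 1, sub-study 4, section 4.5: 90-day mortality 0.28 in controls with normal TAPSE. Using 0.28 for patients without mottling is an assumption.

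**Formula for two proportions.** Power = Φ[(|p2 − p1| − z·SE0)/SE1]. SE0 = √{p̄(1 − p̄)(1/580 + 1/495)}, where p̄ is the weighted mean rate. SE1 = √{p1(1 − p1)/580 + p2(1 − p2)/495}.

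**The plan's own mortality figure, 0.18 v 0.27.** p̄ = 0.2214, SE0 = 0.02541, SE1 = 0.02555. Power = Φ[(0.09 − 2.432 × 0.02541)/0.02555] = Φ(1.10) = 0.865 (simulation 0.866). The stated 0.84 is slightly lower. An alternative of 0.2675, which rounds to 0.27, gives 0.844, and a continuity correction gives 0.849. The gap is small and on the cautious side; it is not part of this point.

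**The plan's own slope figures.** Power ≈ Φ(slope × SDx × √1075/0.99 − 2.432). Urine output: 0.10 × 0.98 × 32.79/0.99 = 3.246, so Φ(0.81) = 0.79 (stated 0.81). Capillary refill time: 0.10 × 2.4 × 32.79/0.99 = 7.95, so 1.00, as stated.

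**A 5-point rise in mortality.**

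- 0.18 v 0.23: SE0 = 0.02461, SE1 = 0.02474; Φ[(0.05 − 0.05986)/0.02474] = Φ(−0.40) = 0.345 (simulation 0.347).
- 0.28 v 0.33: SE0 = 0.02812, SE1 = 0.02818; Φ[(0.05 − 0.06840)/0.02818] = Φ(−0.65) = 0.257 (simulation 0.256).

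**Other readings of 5%.**

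| Reading | Control 0.18 | Control 0.28 |
|---|---|---|
| 5-point rise, alpha 0.015 | 0.34 | 0.26 |
| 5-point fall, alpha 0.015 | 0.43 | 0.29 |
| 5-point rise, alpha 0.05 | 0.53 | 0.43 |
| 5-point fall, alpha 0.05 | 0.61 | 0.46 |
| 5% relative rise, alpha 0.015 | 0.02 | 0.03 |

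A slope of 0.05 in cardiac index has power 0.21 for urine output and 0.94 for capillary refill time.

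**What is detectable.** At 80% power the smallest rise is 8.3 points from 0.18 and 9.4 points from 0.28. Detecting 5 points at 80% power would take about 2,800 patients (from 0.18) or 3,650 (from 0.28), against 1,075.

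**The missing 90-day figure.** Its size depends on the control rate and the effect scale, and the SAP fixes neither for this comparison. The control rates below are assumptions. The hazard ratio implied by 0.18 v 0.27 is ln(0.73)/ln(0.82) = 1.59.

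| Assumed 90-day control rate | Constant 9 points | Constant hazard ratio 1.59 |
|---|---|---|
| 0.22 | 0.82 | 0.93 |
| 0.28 | 0.76 | 0.97 |
| 0.35 | 0.72 | 0.99 |

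The results lie on both sides of 0.84, so the mismatch in time point cannot be called a loss or a gain in power.

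**The case against.** The strongest reply is that the clause is one line in a discussion. Section 3.2 openly gives the effects and powers, presents them as examples, and says the sample size could not be derived from earlier studies. The primary prognostic analysis is a multivariable Cox model, so a crude two-group test does not define what the cohort can detect. Section 7 itself stresses that results are hypothesis-generating. This limits the consequence, but it does not make the sentence true. If Section 3.2 is only illustrative, it supports a general 5% claim even less.

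Second, for the diagnostic outcome 5% cannot be called false. No mean cardiac index is given, so a 5% difference in it cannot be checked, and a slope of 0.05 on capillary refill time does have power 0.94. That is fair: for cardiac index the claim is unsupported rather than refuted. One favourable predictor still cannot carry a statement about both primary outcomes.

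Third, the 0.26 to 0.34 range assumes an increase in mortality and, at its lower end, a borrowed control rate. A decrease gives 0.29 to 0.43. That widens the range but leaves it far below 0.80.

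Fourth, the 30-day versus 90-day mismatch is a separate matter with no demonstrated loss of power. This stands as to size. The mismatch still belongs here, because Section 7 claims a result for the primary outcomes.

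**Conclusion.** The concern holds. The 5% statement in Section 7 has no counterpart in Section 3.2. For mortality it is also numerically wrong: power for a 5-point rise is about 0.34 (control 0.18) or 0.26 (control 0.28), so such a difference would be missed roughly two times in three or more. A 5-point fall from 0.18 would be missed 57% of the time. These figures rest on the mottling split of 495 and 580, a two-sided alpha of 0.015 and an unadjusted comparison; 0.28 is borrowed from a sub-study. The conclusion does not depend on these choices, since no mortality reading tabulated above exceeds 0.61. For cardiac index the claim is unsupported and cannot be checked. Power for 90-day mortality, the primary prognostic outcome, is not given. This should be fixed, but it does not put the design or the analyses in doubt.

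**What to change.** 1. **Section 7:** delete the 5% clause and state the effects calculated in 3.2. Suggested wording: with 1075 patients and a threshold of 0.015, stated power is 0.84 for 30-day mortality of 0.18 versus 0.27 (skin mottling example), and 0.81 (urine output) and 1.00 (capillary refill time) for a slope of 0.10 in cardiac index. When repeating 0.84, confirm the unrounded inputs, because the printed ones give 0.865. If the authors did have a separate 5% calculation, it should be added to 3.2 with its inputs.
2. **Section 3.2.2:** label the mottling example as a 30-day, secondary time point.
3. **Section 3.2.2, desirable but optional:** add a 90-day line that states the assumed control rate and effect scale and shows a range. With an assumed control rate of 0.28, for example, power is 0.76 for a constant 9-point difference and about 0.97 for a constant hazard ratio of 1.59.

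The cost is one clause in Section 7, a label and at most one added line in 3.2.2. Sample size, threshold, models and analyses stay as they are.
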